5.2 Important steps for cohort formation

New users (defined as no use in 180 days prior to index date) of an exposure and a comparator drug will be identified.

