5.2.2 Specify inclusion/exclusion criteria for cohort entry and define the index date

Inclusion and exclusion criteria were adapted from the trial as closely as possible. Definitions for all inclusion/exclusion are provided in **Appendix A** and are summarized in the flowcharts below.

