5.3 Flowchart of the study cohort assembly

For dabigatran 150mg vs. warfarin

	Optum		Truven		Medicare	
	Less Excluded Patients	Remaining Patients	Less Excluded Patients	Remaining Patients	Less Excluded Patients	Remaining Patients
All patients		77,673,639		200,203,908		6,886,908
Did not meet cohort entry criteria	76,847,731	825,908	199,014,982	1,188,926	-2,335,930	4,550,978

Excluded due to insufficient enrollment	-80,642	745,266	-107,905	1,081,021	-1,565,261	2,985,717
Excluded due to prior use of referent	-564,968	180,298	-751,832	329,189	-2,241,426	744,291
Excluded due to prior use of exposure	-44,640	135,658	-71,891	257,298	-196,688	547,603
Excluded because patient qualified in >1 exposure category	-5	135,653	-9	257,289	-24	547,579
Excluded based on Dabigatran (dose other than 150mg)	-306	135,347	-534	256,755	-2,557	545,022
Excluded based on Age	0	135,347	0	256,755	-162	544,860
Excluded based on Gender	0	135,347	0	256,755	0	544,860
Excluded based on Inclusion 1a or 1b or 1 c - Atrial fibrillation	-71,189	64,158	-135,349	121,406	-220,602	324,258
Excluded based on Inclusion 2a-2e History of Stroke, TIA, Systemic embolism / EF<40% / NYHA 2 or higher / Age >75 / Age 65+RF	-11,313	52,845	-17,737	103,669	-24,940	299,318
Excluded based on Inclusion 3 - Age >= 18	-1	52,844	-1	103,668	0	299,318
Excluded based on Exclusion 1 - History of heart valve disorders	-17,688	35,156	-5,687	97,981	-94,948	204,370
Excluded based on Exclusion 2a - Severe/disabling stroke	-576	34,580	-1,111	96,870	-3,090	201,280
Excluded based on Exclusion 2b - Any stroke	-960	33,620	-1,391	95,479	-3,948	197,332
Excluded based on Exclusion 3a - Major Surgery	-1,091	32,529	-2,526	92,953	-6,491	190,841
Excluded based on Exclusion 3c - Intracranial hemorrhage - Inpatient	-51	32,478	-331	92,622	-595	190,246
Excluded based on Exclusion 3d - Gastrointestinal hemorrhage	-4,848	27,630	-1,601	91,021	-5,353	184,893
Excluded based on Exclusion 3e - Symptomatic or endoscopically documented gastroduodenal ulcer disease	-121	27,509	-714	90,307	-3,148	181,745
Excluded based on Exclusion 3f - Hemorrhagic disorder or bleeding diathesis	-257	27,252	-756	89,551	-1,787	179,958
Excluded based on Exclusion 3i - Uncontrolled hypertension	-51	27,201	-400	89,151	-804	179,154

Excluded based on Exclusion 7 - Severe renal impairment	-1,301	25,900	-4,674	84,477	-12,016	167,138
Excluded based on Exclusion 8 & 9 - Active infective endocarditis and liver disease	-36	25,864	-255	84,222	-616	166,522

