Excluded based on Exclusion 10 & 11 - Pregnancy & Anemia and Thrombocytopenia	-191	25,673	-1,229	82,993	-2,798	163,724
Excluded based on Exclusion 14 - Alcohol abuse or dependence	-28	25,645	-103	82,890	-138	163,586
Excluded based on Exclusion 14 - Drug abuse or dependence	-22	25,623	-47	82,843	-111	163,475
Excluded based on Exclusion 14 - CCI (180 days)	-7	25,616	-47	82,796	-1,939	161,536
Final cohort		25,616		82,796		161,536

* Medicare database includes all patients using a novel oral anticoagulant and a subset of patients using warfarin during 2011-2017.

6. Variables

6.1 Exposure-related variables:

Study drug:

The study exposure of interest is initiation of dabigatran. Initiation will be defined by no use of dabigatran or a comparator in the prior 6 months before treatment initiation (washout period).

Comparator agents-

- Initiators of dabigatran (150mg) will be compared to initiators of-
 - Warfarin

6.2 Covariates:

- Age
- Sex
- Combined Comorbidity Index (CCI), measured over the baseline covariate assessment period, defined as 180 days prior to and including index date

Covariates listed above represent only a small subset of covariates that will ultimately be controlled for in the design and analysis. We use the covariates above only for initial feasibility analyses to judge whether there is likely to be sufficient overlap between treatment groups to proceed with the study. Remaining covariates are defined only after the study has passed the initial feasibility analysis and the initial power assessment and are listed in Table 1 (**Appendix B**).

6.3 Outcome variables and study follow-up:

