6.3.2 Study follow-up

Both as-treated (AT) and intention-to-treat (ITT) analyses will be conducted with treatment defined as the index drug on the day of cohort entry. Because adherence in the real-world databases is expected to be much worse than in the trial, the AT analysis is the **primary** analysis, as it targets the relative hazard of outcomes on treatment.

For the AT analyses, the follow-up will start the day after initiation of apixaban and comparator and will continue until the earliest date of the following events:

- The first occurrence of the outcome of interest, unless otherwise specified for selected outcomes,
- The date of end of continuous registration in the database,
- End of the study period,
- Measured death event occurs,

- Nursing home admission
 - Nursing home admissions are considered a censoring event because the data sources utilized typically provide little to no data on a patient, particularly on drug utilization, after admission. We will utilize this as an exclusion reason for cohorts for the same reason.
- The date of drug discontinuation, defined as the date of the last continuous treatment episode of the index drug (dabigatran and comparator) plus a defined grace period (i.e., 10 days after the end of the last prescription's days' supply in main analyses).
- The date of augmentation or switching from exposure to comparator or vice versa or augmentation/switching to any other NOAC (e.g. switching from dabigatran or warfarin to apixaban would be a censoring event);
 - A dosage change on the index treatment does not fulfill this criterion
 - An added treatment that is not part of the exposure or comparator group does not fulfill this criterion
- Dispensing of a fibrinolytic agent

For the intention-to-treat (ITT) analyses, the censoring based on the augmentation/switching and treatment discontinuation will be replaced with a maximum allowed follow-up time of 365 days.

7. Initial Feasibility Analysis

Action report name:

For dabigatran vs. warfarin

Optum- <https://bwh-dope.aetion.com/projects/details/707/results/59579/result/0>

Marketscan- <https://bwh-dope.aetion.com/projects/details/708/results/59601/result/0>

Medicare- <https://bwh-dope.aetion.com/projects/details/709/results/59602/result/0>

Date conducted: 10/5/20 (Medicare 10/6/20)

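### The 180-day washout names only dabigatran and warfarin, so recent users of another NOAC can enter either arm as initiators, and no readable Table 1 row adjusts for it

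*Combined protocol and SAP*

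**What the plan says.** - Section 5.2: "New users (defined as no use in 180 days prior to index date) of an exposure and a comparator drug will be identified".
- Section 6.1: "Initiation will be defined by no use of dabigatran or a comparator in the prior 6 months before treatment initiation (washout period". The comparator list under it has one entry, warfarin.
- Section 5.2.2: "Definitions for all inclusion/exclusion are provided in" Appendix A. That appendix has no item on prior apixaban, rivaroxaban or edoxaban. The nearest, 3g, concerns anticoagulation needed for another disorder and is marked N/A.
- Section 5.3 has two prior-use rows, "Excluded due to prior use of referent" and "Excluded due to prior use of exposure". Above them is a row that is not broken down, "Did not meet cohort entry criteria". The footnote says that the Medicare extract holds all NOAC users.
- Section 6.3.2, as-treated (AT, primary): "switching from dabigatran or warfarin to apixaban would be a censoring event". For ITT, "the censoring based on the augmentation/switching and treatment discontinuation will be replaced with a maximum allowed follow-up time of 365 days".
- Appendix B, Table 1: the readable rows on prior anticoagulants are heparin/LMWH, fondaparinux or bivalirudin, and other direct thrombin inhibitors. Antiplatelet agents are listed as well. No readable row covers an oral factor Xa inhibitor.

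**The concern.** The plan treats another NOAC as changing the exposure after index but has no stated rule for the same drugs before index. A patient who took apixaban last month and fills dabigatran or warfarin today meets the written definition of an initiator. That patient is continuing oral anticoagulation, not starting it.

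Recent use of another NOAC could relate both to the choice of index drug and to the risk of stroke or bleeding. If its frequency differs between the arms after matching, and if it carries risk beyond the measured covariates, the hazard ratio is confounded by a variable that nothing visible in the plan measures. The drugs can be identified in these data, because the censoring rule depends on them.

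**Working it through.** **1. Scope of the rule.** Sections 5.2 and 6.1 agree: the exposure and the comparator, over 180 days or 6 months. With warfarin the only comparator, two drugs are washed out.

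**2. Flowchart.** Starting from the count left after the entry-criteria row in section 5.3 and subtracting every listed row:

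| | Optum | MarketScan | Medicare |
|---|---|---|---|
| After entry criteria | 825,908 | 1,188,926 | 4,550,978 |
| Insufficient enrollment | 80,642 | 107,905 | 1,565,261 |
| Prior warfarin | 564,968 | 751,832 | 2,241,426 |
| Prior dabigatran | 44,640 | 71,891 | 196,688 |
| All later rows, summed | 110,042 | 174,502 | 386,067 |
| Remainder | 25,616 | 82,796 | 161,536 |
| Unmatched Table 1 | 25,601 | 82,719 | 161,317 |
| Difference | 15 | 77 | 219 |

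The remainders equal the stated final cohorts. No prior-NOAC row lies between the entry-criteria row and the final cohort, and no large step follows it (15 + 77 + 219 = 311 patients, not explained).

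**3. What this does not show.** The subtraction says nothing about the entry-criteria row itself. Nor does it show which drugs the two prior-use rows cover in practice: their sum equals the drop across them whatever the washout contains.

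**4. Post-index switching.** The section 9 censoring rows add up to the matched total: 0 + 657 + 2,760 + 62,039 + 2,483 + 4,128 + 6,073 = 78,140. Each patient is therefore counted once, at the first event. The row for other-NOAC switch or nursing home is 6,073/78,140 = 7.77%. End of index exposure is 62,039/78,140 = 79.39%. A patient who starts another NOAC after that point is not in the 7.77%.

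**5. Possible size (assumptions only).** Let p1 and p0 be the shares of prior other-NOAC users on dabigatran and warfarin, and R their outcome-rate ratio that remains after matching. The hazard ratio is multiplied by (1 + p1(R − 1)) / (1 + p0(R − 1)).

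- 5% against 2%, R = 1.5: 1.025/1.010 = 1.015, or 0.985 with the arms reversed. An HR of 0.66 reads 0.67 or 0.65.
- 15% against 5%, R = 2: 1.15/1.05 = 1.095, or 0.913 reversed. An HR of 0.66 reads 0.72 or 0.60.
- Equal shares: no shift.

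The documents supply neither the shares nor R.

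**6. Power.** With d events and 1:1 matching, power = Φ(|ln HR|·√d/2 − 1.96), using HR 0.66 for superiority and the margin 1.46 for non-inferiority (section 10). For the pooled data d = 78,140 × 5.64/1,000 = 440.71:

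- Superiority: 0.4155 × 10.4965 − 1.96 = 2.40, giving 0.992 (plan: 0.9918).
- Non-inferiority: 0.3784 × 10.4965 − 1.96 = 2.01, giving 0.978 (plan: 0.9779).

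The plan's figures are reproduced. Under an assumed loss of events in a restricted analysis (superiority/non-inferiority):

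| | Plan | 10% fewer | 20% fewer |
|---|---|---|---|
| Pooled | 0.992/0.978 | 0.985/0.965 | 0.974/0.944 |
| Medicare | 0.927/0.874 | 0.899/0.838 | 0.862/0.794 |
| MarketScan | 0.707/0.626 | 0.661/0.580 | 0.610/0.532 |

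Optum, at about 0.18/0.16, is underpowered in any case.

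**The case against.** **The exclusion may exist without being shown.** Figure 1 is not readable. The Table 1 medication rows between antidepressants and anxiolytics are lost from both the unmatched and the matched tables. The entry-criteria row is not itemised. Section 6.3.2 also says that nursing home admission will be used to exclude patients from the cohorts, yet it has no Appendix A item and no flowchart row. This stands: a stated exclusion can be absent from both lists, so their silence on prior NOACs is not proof. A reader might infer from the exact flowchart sums that recent NOAC users are certainly in the cohort. The sums do not support that.

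**Much of the risk is already controlled.** Appendix A excludes recent GI hemorrhage, prior inpatient intracranial hemorrhage, stroke within 14 days and CKD stage 4/5 or ESRD. Matched pooled values are close: any stroke 7.9% against 7.8%, HAS-BLED 3.27 against 3.27, CHADS2 2.47 against 2.48. This makes a large R less plausible. It does not identify prior NOAC use or show that it is balanced.

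**A two-drug washout is a recognised new-user design.** The trial criteria reproduced in Appendix A do not require patients to be free of prior oral anticoagulants. This stands as a reason not to insist on a wider primary washout. It is not a reason to leave prior use unmeasured.

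**ITT.** A reader might infer that the ITT analysis is specially damaged, because a patient who returns to the earlier NOAC stays in the index arm. Keeping switchers is inherent to ITT and applies to all of them; the washout does not cause it.

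**Conclusion.** The point holds as a gap in the written rule. Sections 5.2 and 6.1 admit recent users of another NOAC to either arm, and nothing readable in Appendix A, the flowchart or Table 1 excludes or adjusts for them. It rests on the readable text and would be closed by one sentence pointing to an exclusion or a PS term already in place.

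No size or direction of bias is established. The illustration runs from a shift of about 1.5% to about 9%, either way, on assumed inputs. A reader might take 7.77% as an upper bound on switching or as a guide to prior use. It is neither: it counts first censoring events only, combines switching with nursing home admission, and describes the period after index. Confidence is medium, and the matter should be settled before the comparative analysis.

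**What to change.** Before the comparative analysis:

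1. State in 5.2 and 6.1 whether use of another NOAC in the 180 days before index is already excluded or already in the PS, and where.
2. If neither, report prior apixaban, rivaroxaban and edoxaban use by arm and database, before and after matching, within the section 9 step. That step uses a dummy outcome, so no comparative result is exposed.
3. Add prior other-NOAC use to the PS and Table 1 where the counts allow.
4. Pre-specify under 13.2, which has no entry yet, a sensitivity analysis (AT and ITT) restricted to patients with no oral anticoagulant in the prior 180 days.

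The primary washout need not be widened: no count or direction of bias in the documents would justify that trade-off.

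Cost: the PS re-run in three databases produces a new matched cohort. The section 9 balance table and the section 10 matched counts and power must then be updated and pass again through the review stop that closes section 10. The restricted analysis loses some events. Pooled power remains high under the assumed losses, but the MarketScan estimate becomes less informative and should be read with the pooled one.

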6.3.1 Outcome variables

Primary Effectiveness outcomes of interest: (definitions provided in **Appendix A**):

- **Primary Outcome:** Stroke (hemorrhagic, ischemic) and systemic embolism
- **Secondary outcomes:** Individual components
 - Hospital admission for stroke (principal diagnosis position)
 - Hospital admission for systemic embolism (principal diagnosis position)

Control outcomes of interest (control outcomes only serve to assess aspects of study validity but are not further interpreted):

1. Major bleeding

6.3.2 Study follow-up

Both as-treated (AT) and intention-to-treat (ITT) analyses will be conducted with treatment defined as the index drug on the day of cohort entry. Because adherence in the real-world databases is expected to be much worse than in the trial, the AT analysis is the **primary** analysis, as it targets the relative hazard of outcomes on treatment.

For the AT analyses, the follow-up will start the day after initiation of apixaban and comparator and will continue until the earliest date of the following events:

- The first occurrence of the outcome of interest, unless otherwise specified for selected outcomes,
- The date of end of continuous registration in the database,
- End of the study period,
- Measured death event occurs,

- Nursing home admission
 - Nursing home admissions are considered a censoring event because the data sources utilized typically provide little to no data on a patient, particularly on drug utilization, after admission. We will utilize this as an exclusion reason for cohorts for the same reason.
- The date of drug discontinuation, defined as the date of the last continuous treatment episode of the index drug (dabigatran and comparator) plus a defined grace period (i.e., 10 days after the end of the last prescription's days' supply in main analyses).
- The date of augmentation or switching from exposure to comparator or vice versa or augmentation/switching to any other NOAC (e.g. switching from dabigatran or warfarin to apixaban would be a censoring event);
 - A dosage change on the index treatment does not fulfill this criterion
 - An added treatment that is not part of the exposure or comparator group does not fulfill this criterion
- Dispensing of a fibrinolytic agent

For the intention-to-treat (ITT) analyses, the censoring based on the augmentation/switching and treatment discontinuation will be replaced with a maximum allowed follow-up time of 365 days.

7. Initial Feasibility Analysis

Action report name:

For dabigatran vs. warfarin

Optum- <https://bwh-dope.aetion.com/projects/details/707/results/59579/result/0>

Marketscan- <https://bwh-dope.aetion.com/projects/details/708/results/59601/result/0>

Medicare- <https://bwh-dope.aetion.com/projects/details/709/results/59602/result/0>

Date conducted: 10/5/20 (Medicare 10/6/20)

Complete Aetion feasibility analysis using age, sex, and CCI as the only covariates and the primary endpoint (Section 6.3.1) as the outcome. No measures of association will be computed nor will incidence rates stratified by treatment group.

- Report patient characteristics by treatment group
- Report summary parameters of study population
- Report median follow-up time by treatment group
- Report reasons for censoring in the overall study population

8. Initial Power Assessment

Action report name:

For dabigatran vs. warfarin

Optum- <https://bwh-dope.aetion.com/projects/details/707/results/53772/result/0>

Marketscan- <https://bwh-dope.aetion.com/projects/details/708/results/53771/result/0>

Medicare- <https://bwh-dope.aetion.com/projects/details/709/results/53770/result/0>

Date conducted: 05/11/2020

In order to complete the initial power analysis, the dummy outcome of a 90-day gap in database enrollment will be used. This outcome is used to ensure that no information on the comparative risks of the outcomes of interest are available at this stage. Complete a 1:1 PS-matched comparative analysis using this outcome. PS should include only 3 covariates: age, sex, and combined comorbidity index. Power calculations are based on the formulas from Chow et al. (2008).

- Stop analyses until feasibility and power are reviewed by primary investigators and FDA. Reviewers evaluate the results of the analyses described above in Sections 7 and 8, including numbers of patients, patient characteristics, follow-up time, and reasons for censoring by treatment group, as well as overall rates of outcomes and study power. These parameters are re-evaluated and reported in the subsequent sections, after incorporating feedback and refining the protocol.
- Stop analyses until feasibility and power are reviewed by primary investigators, FDA, and assigned members of advisory board.

Reviewed by PI:	[name]	Date reviewed:	6/3/20
Reviewed by FDA:	[name]	Date reviewed:	6/30/20
Reasons for stopping analysis (if required):			

9. Balance Assessment

Action report links:

Optum: <https://bwh-dope.aetion.com/projects/details/707/results/59580/result/0>

Marketscan: <https://bwh-dope.aetion.com/projects/details/708/results/59603/result/0>

Medicare: <https://bwh-dope.aetion.com/projects/details/709/results/59604/result/0>

Date conducted: 10/5/20 (Medicare 10/6/20)

After review of initial feasibility and power analyses, complete creation of the remaining covariates (see Table 1 below for list of covariates). Again, using the dummy outcome of a 90-day gap in database enrollment, complete a 1:1 PS-matched analysis. The PS should include the complete list of covariates (excluding laboratory values, which are missing in some patients).

- Provide plot of PS distributions stratified by treatment group.

Note- Please refer to **Appendix B**.

- Report covariate balance after matching.

Note- For Table 1, please refer to **Appendix B**.

- Report reasons for censoring by treatment group.

	Overall	Referent	Exposure
Dummy Outcome	0 (0.00%)	0 (0.00%)	0 (0.00%)
Death	657 (0.84%)	369 (0.94%)	288 (0.74%)
Start of an additional exposure	2,760 (3.53%)	1,189 (3.04%)	1,571 (4.02%)
End of index exposure	62,039 (79.39%)	31,190 (79.83%)	30,849 (78.96%)
Specified date reached (Dec 17/Dec 18/Dec 19)	2,483 (3.18%)	1,281 (3.28%)	1,202 (3.08%)
End of patient enrollment	4,128 (5.28%)	1,938 (4.96%)	2,190 (5.61%)
Switch to other NOACs (for censoring) + nursing home admission	6,073 (7.77%)	3,103 (7.94%)	2,970 (7.60%)

- Report follow-up time by treatment group.

Median Follow-Up Time (Days) [IQR]			
Patient Group	Optum	Truven	Medicare
Overall Patient Population	98 [38-191]	98 [38-193]	98 [38-202]

Referent	98 [43-192]	98 [43-178]	98 [42-196]
Exposure	98 [38-190]	98 [38-220]	98 [38-211]

- Report overall risk of the primary outcome.

	Optum	MarketScan	Medicare	Pooled
Risk per 1,000 patients	4.57	5.20	6.04	5.64

10. Final Power Assessment

Date conducted:

- Re-calculate power in the appropriate excel table, using the revised number of matched patients from the PS-match in Section 9. All other parameters in the table should be the same as in Section 8. If the study is to be implemented in more than one database, copy and paste excel sheet to report power for each database separately and for the pooled analysis that uses data from all databases together. Power calculations are based on the formulas from Chow et al. (2008).
 - For dabigatran 150mg vs. warfarin
 - Pooled

Superiority Analysis		Non-inferiority Analysis	
Number of patients matched	78,140	Number of patients matched	78,140
Reference	39,070	Reference	39,070
Exposed	39,070	Exposed	39,070
Risk per 1,000 patients	5.64	Risk per 1,000 patients	5.64
Desired HR from RCT	0.66	Assumed HR from RCT	1
Alpha (2-sided)	0.05	Alpha (2-sided)	0.05
		Non-inferiority margin	1.46
Number of events expected	440.7096	Number of events expected	440.7096
Power	0.991836251	Power	0.977906369

- Optum

Superiority Analysis		Non-inferiority Analysis	
Number of patients matched	5,580	Number of patients matched	5,580
Reference	2,790	Reference	2,790
Exposed	2,790	Exposed	2,790
Risk per 1,000 patients	4.57	Risk per 1,000 patients	4.57
Desired HR from RCT	0.66	Assumed HR from RCT	1
Alpha (2-sided)	0.05	Alpha (2-sided)	0.05
		Non-inferiority margin	1.46
Number of events expected	25.5006	Number of events expected	25.5006
Power	0.182503488	Power	0.157581463

- MarketScan

Superiority Analysis		Non-inferiority Analysis	
Number of patients matched	27,920	Number of patients matched	27,920
Reference	13,960	Reference	13,960
Exposed	13,960	Exposed	13,960
Risk per 1,000 patients	5.20	Risk per 1,000 patients	5.20
Desired HR from RCT	0.66	Assumed HR from RCT	1
Alpha (2-sided)	0.05	Alpha (2-sided)	0.05
		Non-inferiority margin	1.46
Number of events expected	145.184	Number of events expected	145.184
Power	0.70656205	Power	0.625504572

- Medicare

Superiority Analysis		Non-inferiority Analysis	
Number of patients matched	44,640	Number of patients matched	44,640
Reference	22,320	Reference	22,320
Exposed	22,320	Exposed	22,320
Risk per 1,000 patients	6.04	Risk per 1,000 patients	6.04
Desired HR from RCT	0.66	Assumed HR from RCT	1
Alpha (2-sided)	0.05	Alpha (2-sided)	0.05
		Non-inferiority margin	1.46
Number of events expected	269.6256	Number of events expected	269.6256
Power	0.926676361	Power	0.874319968

- Stop analyses until balance and final power assessment are reviewed by primary investigators, FDA, and assigned members of advisory board.

Reviewed by PI:	[name]	Date reviewed:	9/8/20
Reviewed by FDA:	[name]	Date reviewed:	9/29/20
Reasons for stopping analysis (if required):			

11. Study Confidence and Concerns

Deadline for voting on study confidence and listing concerns:

Date votes and concerns are summarized:

- If final feasibility and power analyses are reviewed and approved, proceed to the remaining protocol steps.
- All study team and advisory board members that review this protocol should at this stage provide their level of confidence for the success of the RWD study in the [Google Form](#). This form also provides space for reviewers to list any concerns that they feel may contribute to a failure to replicate the findings of the RCT, including differences in study populations, poor measurement of study variables, or residual confounding. All responses will be kept confidential and individual-level results will only be shared with the individual respondent.
- After the deadline for voting has passed, provide the distribution of responses and summarize all concerns here.

12. Register study protocol on clinicalTrials.gov

Date conducted:

- Register the study on [clinicalTrials.gov](#) and upload this document.

13. Comparative Analyses

Action report name:

Date conducted:

13.1 For primary analysis:

13.2 For sensitivity analyses:

14. Requested Results

